2.0 Schedule of Study Assessments *

Procedure	Screening ≤ 28days from Baseline (First day study drug administration)	Cycle 1			Even Cycles	Odd Cycles starting at cycle 3	Discontinuation From Study Drug	End of Study safety assessment	Follow- Up Phase
		Day 1 ¹⁹	Day 8 ¹⁹	Day 15 ¹⁹	Day 22 ¹⁹				
Record prior medications, treatments	X								
Record prior anti-cancer therapies	X								
Physical examination, vital signs, weight *	X	X ¹⁰				X	X	X ¹¹	X
ECOG performance status *	X	X ¹⁰				X	X	X ¹¹	X
CT or MRI of the chest & abdomen / pelvis ^{8,9}	X						X ²¹	X	
Chest x-ray ¹⁸	X						X	X	
Bone survey ¹	X						X	X	
CT or MRI of the brain ²	X						X	X	
Bone marrow aspirate and biopsy (unilateral) ¹⁷	X								
ECG	X							X	
Hematology ³	X	X ¹⁰			X	X	X	X ¹¹	X
Serum chemistry ⁴	X	X ¹⁰			X	X	X	X ¹¹	X
Pregnancy testing ⁵	X ⁶	X ⁶	X ⁶	X ⁶	X ⁶	X ⁶	X ⁶	X ⁶	
Pomalidomide Counseling ⁷		X				X	X	X	
Baseline lesion assessment	X								
Dispense Cycle 1 study drug ^{12, 15}		X							
Response assessment labs ^{13, 14}	X	X				X	X	X	
Record adverse events ¹¹	X	X		X	X	X	X	X ¹¹	X
Record concomitant therapies/procedures				X	X	X	X		
Dispense study drug for next cycle ^{12, 15}					X	X			
Perform drug accountability					X	X	X		
Obtain Follow-Up anti-cancer treatments ¹⁶									X
Obtain Follow-Up survival information ¹⁶									X
Hep B surface antigen ²⁰	X								
Hep C antibody ²⁰	X								

* If Physical examination, vital signs, weight and ECOG performance status were done within 7 days of Day 1, they do not need to be repeated at Study Day 1.

An unscheduled visit can occur at any time during the study. Source must be maintained for these unscheduled visits. The date for the visit and any data generated must be recorded on the appropriate CRF. Source documents for these unscheduled visits must also be maintained.

¹If subject had previously positive bone survey or if symptoms suggest metastases.

²This will only be performed if symptoms raise suspicion of CNS lesions.

³Complete blood count with differential, PT and PTT (within 5 days prior to Day 1 of each cycle); If PT and PTT are within normal limits at screening, and patient is not on anticoagulant therapy that affects these levels, they need only be repeated at discontinuation of study drug.

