¹⁰If screening assessments were done within 7 days of Cycle 1, Day 1, they do not need to be repeated on Cycle 1, Day 1.

¹¹An additional safety assessment will be done 30 days (+/- 1 week) following the last dose of study drug.

¹²Only enough pomalidomide for 1 cycle of therapy may be provided to the patient each cycle.

¹³Serum and urine protein electrophoresis; Quantitative serum IgG, IgA, and IgM; Free serum kappa and lambda light chains; Serum and urine immunofixation studies will be performed at screening, and to evaluate for and confirm CR. Response assessment labs should be performed within 5 days prior to Day 1 of each cycle.

¹⁴All PRs and CRs must be confirmed by repeat Response Assessment labs no less than 6 weeks after the criteria for response are first met.

¹⁵Day 1 may be delayed up to 7 days to accommodate holidays/weekends/inclement weather and other unforeseen events.

¹⁶Information may be obtained without having the subject visit the study center (i.e. phone call).

¹⁷To be repeated if a complete remission is suspected

¹⁸ Chest x-ray will only be performed as part of the screening evaluation and when CR/MRI of the chest is indicated as part of the patient's restaging evaluation.

¹⁹ Assessments to be performed at Cycle 1 Days 1, 8, 15 and 22 may be performed +/- 2 business days from the planned date to accommodate holidays, inclement weather and other unforeseen events.

²⁰ Hep B -we will check Hep B surface antigen. If positive, we will check Hep B surface antibody and Hep B viral DNA. If Hep B surface antibody is negative and/or Hep B viral DNA shows circulating virus, patient will be excluded ; Hep C – we will check Hep C Antibody. If positive, we will check Hep C Viral PCR. If it shows circulating virus, patient will be excluded

²¹ Starting with Cycle 3, CT scans will be performed every 4 months for the first 2 years, every 6 months for the next 2 years, and then once a year thereafter.

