4.2 POMALIDOMIDE

Pomalidomide is an IMiD analogue of thalidomide that, among other anti-tumor properties, on an equimolar basis *in vitro*, displays equivalent anti-angiogenic activity, about 8-fold greater activity in stimulation of apoptosis, at least 10-fold greater activity in inhibition of cellular COX-2 production and over 4,000-fold greater activity in inhibition of cellular TNF-alpha production relative to thalidomide.^{20,21} Pomalidomide has also been shown to stimulate antibody-dependent cytotoxic T-cell activity (ADCC).²⁰

At tolerated doses (MTD = 2 mg QD and 5 mg QOD), pomalidomide has been shown to be active in subjects with relapsed or refractory multiple myeloma (MM).^{20,22,23} In 45 subjects who received doses of pomalidomide ranging, by cohort, up to 10 mg daily, the most commonly occurring dose-limiting toxicity (DLT) was reversible neutropenia. As with other IMiDs administered to subjects receiving concomitant systemic steroids, deep vein thrombosis (DVT) was seen (in 1 subject each in this study and in its subsequent named patient supply rollover program).^{20,24}

Recently, efficacy and safety data from a phase II study, by Lacy et al., were published.⁹ Sixty patients with relapsed or refractory multiple myeloma were enrolled. Pomalidomide was given orally at a dose of 2 mg daily on days 1-28 of a 28-day cycle and dexamethasone was given orally at a dose of 40 mg daily on days 1, 8, 15, 22 of each cycle. Patients also received aspirin 325 mg once daily for thromboprophylaxis. The study endpoints were the response rate in patients taking pomalidomide plus dexamethasone including patients with lenalidomide resistant refractory multiple myeloma, and safety of pomalidomide plus dexamethasone. Thirty eight patients achieved objective response (63%) including CR in 3 patients (5%), VGPR in 17 patients (28%), and PR in 18 patients (30%). The CR + VGPR rate was 33%. Grade 3 or 4 hematologic toxicity occurred in 23 patients (38%) and consisted of anemia in three patients (5%), thrombocytopenia in two patients (3%) and neutropenia in 21 (35%). Among those that developed grade 3/4 neutropenia, all first experienced the neutropenia in cycle 1-3; no new patients experienced grade 3/4 neutropenia in cycle 4 or later. The most common non-hematological grade 3/4

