6.1.1.2 CLINICAL PHARMACOLOGY

Mechanism of Action:

Pomalidomide, a thalidomide analogue, is an immunomodulatory agent that, among other anti-tumor properties, on an equimolar basis in vitro, displays equivalent anti-angiogenic activity, about 8-fold greater activity in stimulation of apoptosis, at least 10-fold greater activity in inhibition of cellular COX-2 production and over 4,000-fold greater activity in inhibition of cellular TNF-alpha production relative to thalidomide [9,10]. Pomalidomide has also been shown to stimulate antibody-dependent cytotoxic T-cell activity (ADCC) [11].

6.1.1.3 Dose and tolerability:

Pomalidomide was safe at doses of up to 50 mg in a phase 1 single dose study in normal, healthy male volunteers and up to 5 mg QOD or 2 mg QD in a phase 1 multi-dose clinical study in subjects with relapsed or refractory multiple myeloma; DLTs seen in subjects receiving higher doses were predominantly hematopoietic (i.e., neutropenia), and lower grade, self-limited neutropenia was also seen in some of the 1 and 2 mg QD and 5 mg QOD recipients. In a multi-dose, phase 2 clinical study of subjects with prostate cancer, 2 mg QD dosing was well tolerated and, unlike the multiple myeloma subjects who received 1 and 2 mg QD doses, only an overall shift to lower neutrophil counts was noted. No clinically relevant neutropenic AEs were observed, and no grade 3 or 4 neutropenic events occurred. It is, therefore, likely that subjects with solid tumors that do not extensively involve the bone marrow will have a higher pomalidomide MTD than subjects with hematologic malignancies.

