6.4 Drug Administration

6.4.1 Treatment assignments

This is a Phase I non-randomized study. Eligible patients will be allocated to treatment in the order in which they sign the informed consent and that all documentation needed to confirm eligibility has been completed. A maximum of 30 subjects will be enrolled and treated with single agent pomalidomide. Starting at dose level 1 in Schedule A, the study will enroll patients in cohorts of 3, following a standard 3 +3 statistical design. (see Section 11.0).

Definition of Dose Limiting Toxicity (DLT):

Toxicity will be evaluated according to the NCI CTCAE version 4.0, (see Appendix E)

1) Non-hematologic dose limiting toxicity (DLT) is defined as any grade ≥ 3 non-hematological toxicity occurring during the first 28 days (first cycle) of treatment, with the specific exception of:

- Isolated Grade 3 elevation of liver function tests (LFTs) without associated clinical symptoms, lasting for ≤ 7 days in duration.
- Isolated Grade 3 elevation of amylase without associated clinical symptoms
- Grade 3 hypocalcemia, hypokalemia, hypomagnesemia, hyponatremia, or hypophosphatemia which responds to medical intervention.

2) Hematological dose limiting toxicity is defined as Grade ≥ 3 neutropenia with fever ≥ 38.5 , Grade 4 neutropenia lasting for ≥ 7 days in duration, or any Grade 4 anemia or thrombocytopenia occurring during the first 28 days (first cycle) of treatment.

Definition of Maximum Tolerated Dose (MTD): MTD is defined as the highest dose level in which 6 patients have been treated with less than 2 instances of DLT.

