6.4.5 Dose Modification or Interruption

Pomalidomide Dose Reductions

Dose reduction(s) will be allowed for any subject who develops a DLT during Cycle 1 or beyond Cycle 1 who develops a toxicity that, in the opinion of the Investigator, requires a dose-reduction.

For treatment interruptions during a cycle, the (28- or 21-day) schedule of each cycle will continue to be followed. Missed doses of pomalidomide are not made up.

For treatment interruptions that delay the scheduled start of a new cycle, when toxicity has resolved as required to allow the start of a new cycle (Section 6.5), the restart day of therapy becomes Day 1 of the next cycle.

The following table provides the dose reduction sequence for pomalidomide:

Table 2: Schedule of Pomalidomide Dose Reduction

	If the DLT/Toxicity occurred or recurred at --- (mg/dose/d 1-28 or d 1-21 depending on Schedule):	Reduce dose to --- (mg/dose/d 1-28 or d 1-21 depending on Schedule):
Pomalidomide	4	3
	3	2
	2	1
	1	0.5

Dosing interruptions and reductions are not permitted during Cycle 1 unless the subject experiences a DLT. Dose interruptions and reductions are permitted beyond Cycle 2. Examples of possible reasons for and extent of dose modification management are outlined in Table 3. The events listed are not all-inclusive and are based on observations pooled from studies with all compounds in the IMiD® class of drugs. Therefore, these events may occur but are not necessarily expected. The investigator may choose to modify pomalidomide dosing further downward or discontinue pomalidomide treatment for any adverse event.

Study drug may be held (up to 21 days) and subsequent dose reductions made as outlined in Table 3. If study drug needs to be held > 21 days, the patient is to be taken off study. Once a dose has been reduced, it cannot be re-escalated.

At the discretion of the Investigator, the use of G-CSF will be permitted to manage neutropenic fever or a Grade 4 neutropenia.

Table 3: Pomalidomide Dosage Modifications for cycles ≥ 2

Common Terminology Criteria (CTCAE) Version 4.0	Adverse Event	Dose Change for Pomalidomide
Allergy/Immunology	Allergic reaction/ hypersensitivity (including drug fever) Grade 2	Hold study drug until resolved to \leq Grade 1; Decrease dose by 1 dose level
Allergy/Immunology	Allergic reaction/ hypersensitivity (including drug fever) Grade 3 or 4	Discontinue Study Drug

Common Terminology Criteria (CTCAE) Version 4.0	Adverse Event	Dose Change for Pomalidomide

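### Cycle 1 DLTs rest on Grade 4 blood counts, but no text fixes a mid-cycle count, and Sections 6.4.1 and 11.1 define the DLT differently

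*Combined protocol and SAP*

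**What the plan says.** - **DLT, Section 6.4.1.** The hematologic criteria for the first 28 days include "Grade 4 neutropenia lasting for ≥ 7 days in duration, or any Grade 4 anemia or thrombocytopenia". They also include Grade 3 or higher "neutropenia with fever ≥ 38.5".
- **DLT, Section 11.1.** The window is the first cycle, given as 28 days on Schedule A and 21 days on Schedule B. The hematologic list has no fever criterion, and it adds any Grade 5 hematologic toxicity, which Section 6.4.1 does not list.
- **Count timing, Section 2, footnote 3.** The complete "blood count with differential, PT and PTT (within 5 days prior to Day 1 of each cycle"). Footnote 10 waives the Cycle 1 Day 1 count if screening was within the preceding 7 days.
- **Cycle 1 visits, footnote 19.** "Assessments to be performed at Cycle 1 Days 1, 8, 15 and 22" may move by 2 business days. The footnote names no assessment.
- **Extra visits, Section 2.** "An unscheduled visit can occur at any time during the study"; none is required.
- **Dosing, Section 6.4.5.** "Dosing interruptions and reductions are not permitted during Cycle 1 unless the subject experiences a DLT".
- **Use of the DLTs, Section 11.1.** Escalate after 0 of 3 or 1 of 6; two or more DLTs exceed the MTD.

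**The concern.** The MTD is the primary endpoint, and each escalation decision turns on one or two events. Two of the criteria need a laboratory value taken at the right time, and one also needs evidence that the value persisted for 7 days. If the only assured sample comes at the end of the cycle, an episode without symptoms that falls and recovers earlier leaves no trace and is scored as no DLT.

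Neutropenia is a foreseeable toxicity here. Section 4.2 reports that in the earlier myeloma study the most common "dose-limiting toxicity (DLT) was reversible neutropenia".

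The two DLT definitions add a separate problem: the same patient can be a DLT under one section and not under the other.

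**Working it through.** **1. What the text requires in Cycle 1.** With 28-day cycles, Cycle 2 Day 1 is Day 29, so footnote 3 places the pre-Cycle 2 count on Days 24-28. Nothing else in the text requires an earlier count:
- The weekly CBC in Table 3 applies to cycles 2 onward, once a cytopenia is known.
- The weekly evaluation in Section 6.5 starts only if the new-cycle criteria fail.
- Unscheduled visits are optional.

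The weekly Cycle 1 pregnancy tests, by contrast, are spelled out in footnote 6.

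**2. What the table can hold.** There are ten column headings and nine surviving cells per row. After Screening and Cycle 1 Day 1, the Hematology row reads blank, blank, X, X, X, X (footnote 11), X. Assume one cell was lost and the order kept. Putting the missing cell, blank or marked, at each of the ten positions never gives more than one mark on Days 8, 15 and 22.

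The rows do not agree on which placement is right. The CT row (footnote 21, starting with Cycle 3) fits a lost last cell, which puts a hematology mark on Day 22. The drug-dispensing and follow-up rows fit a cell lost earlier, which puts none there.

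**3. Direction.** With q the probability that a patient is scored as a DLT, a level passes with probability (1-q)^3 + 3q(1-q)^2 x (1-q)^3. This falls as q rises. Unscored events lower q, so they raise the chance of escalation.

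**4. Illustration of detection.** The documents give no onset or duration, so both are assumed. Onset is uniform on integer days 2-28, 8-28 or 15-28 (27, 21 or 14 values), and the pre-Cycle 2 count is on Day 26. Seen means that a count falls inside the episode. Shown means Grade 4 again at a count at least 7 days after the first Grade 4 count, with a repeat at exactly 7 days.

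Example (14-day episode, onset Days 2-28, Day 26 only): seen if onset is Day 13-26, 14/27 = 52%. Shown if Day 33 is still inside, onset Day 20-26, 7/27 = 26%.

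| Counts | 7-day seen | 14-day seen | 10-day shown | 14-day shown | 21-day shown |
|---|---|---|---|---|---|
| Day 26 only | 26-50% | 52-86% | 11-21% | 26-50% | 52-86% |
| + Day 8 | 38-52% | 71-86% | 19-22% | 38-52% | 71-86% |
| + Day 15 | 52-67% | 86-93% | 22-29% | 52-67% | 86-93% |
| + Day 22 | 41-79% | 67-86% | 22-43% | 41-79% | 67-86% |
| + all three | 86-93% | 86-93% | 44-50% | 86-93% | 86-93% |

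- Episodes of exactly 7 days are shown on no schedule.
- For 21-day episodes, Day 15 alone does as well as all three days.
- With onset on Days 2-21, 14-day episodes are shown in 10% (Day 26 only), 30-45% (one further count) and 100% (all three).
- Without a repeat, 14-day episodes are shown inside Cycle 1 in 0% with Day 26 only or with Day 8 or 22 added, in 7-14% with Day 15 added, and in only 7-52% with all three.

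The last line matters. Much of the gain in the table comes from repeats after Day 28, and the plan does not say whether those count.

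**5. The two definitions.** A qualifying toxicity on Days 22-28 of Schedule B is a DLT under Section 6.4.1 but falls outside the window in Section 11.1. The pre-Cycle 2 sample on Days 24-28 would itself fall after a 21-day window closes. Grade 3 neutropenia with fever of 38.5 or more is a DLT under Section 6.4.1 but is absent from the hematologic list in Section 11.1.

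**The case against.** **The table governs, and it is damaged.** Section 6.3 refers all on-study assessments to the Section 2 schedule, and damage in extraction is not a fault of the plan. This stands. A reader might infer that no count at all is taken between Day 1 and Day 24. The documents do not support that, because one mark, plausibly on Day 22, cannot be excluded. The count part of this point therefore depends on the original table.

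**Other text presupposes counts within a cycle.** Aspirin depends on platelets of at least 50,000, Section 6.5 refers to prophylaxis held during a cycle, and G-CSF is allowed for Grade 4 neutropenia. This is fair, but none of it fixes a day.

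**Many events are caught anyway.** Cytopenia persisting to Days 24-28, febrile neutropenia and symptomatic events largely surface, and sites may draw extra counts. The point is confined to early or short episodes and to duration. It is firmest for neutrophils and platelets, since the CTCAE grade definitions are not reproduced in the protocol.

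**Dosing.** A reader might infer that an unseen event necessarily leaves a patient on full dose. Section 6.4.5 restricts Cycle 1 changes to DLTs, but it also lets the investigator reduce or stop for any adverse event. A Grade 4 neutrophil value is in any case not a DLT until 7 days have passed.

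**Size.** It is tempting to put a detection share into the 3+3 and report a shift in the MTD. That would need a true DLT rate and the share of DLTs that depend on counts, and the documents give neither. The myeloma study ran cohorts up to 10 mg daily, and Section 6.1.1.3 says that "lower grade, self-limited neutropenia was also seen in some of the 1 and 2 mg QD" and 5 mg alternate-day recipients. No Cycle 1 rate of Grade 4 neutropenia lasting 7 days is given for 1-4 mg.

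**Conclusion.** The point holds as something the sponsor should fix, in two parts.

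- **Definitions.** The conflict between Sections 6.4.1 and 11.1 is plain from the text and needs no assumption. The window conflict bites only if Schedule B is opened; the fever conflict applies to both schedules.
- **Counts.** No stated text secures a mid-Cycle 1 count, and the table as extracted holds at most one. The direction, towards too high an MTD, follows provided that an event not seen, or a duration not shown, is scored as no DLT. The size is unknown. The percentages depend on assumed onset, duration and sampling day and compare schedules only; they do not estimate bias in this trial.

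A reader might conclude that the MTD will be materially overstated, or that the plan cannot proceed without this change. The documents support neither.

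**What to change.** 1. Reconcile Sections 6.4.1 and 11.1 so that one DLT window for each schedule and one hematologic DLT list drive the 3+3 decisions. Which version applies is for the sponsor to settle.
2. Check the Hematology row in the original table. If Days 8, 15 and 22 of Cycle 1 are not all marked, add a CBC with differential on those days and amend footnote 3.
3. After a first Grade 4 neutrophil value, schedule a repeat at about 7 days. A repeat merely within 7 days cannot test the criterion.
4. State how duration is dated from the counts, and whether an episode that starts in Cycle 1 and reaches 7 days after Day 28 counts. Added counts do not settle this: even weekly counts with a 7-day repeat show no 7-day episodes and only 44-50% of 10-day ones.

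**Cost.** Two added counts per patient if one day is already marked (2 x 30 = 60), three if none is (3 x 30 = 90), plus repeats. The days already exist in the schedule, but the weekly pregnancy tests apply only to females of childbearing potential, so some patients would need added attendances.

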6.4.2 Dosing regimen

There are four predefined dose levels (1, 2, 3, and 4) for pomalidomide, and two alternative dosing schedules (A and B). With schedule A, patients will be treated with the study drug for 28 days within each cycle. With schedule B, patients will be treated for 21 days within each 28 day cycle. Schedule B will only be explored if the MTD is exceeded at dose level 1 within Schedule A. The first cohort of 3 patients will be treated at dose level 1 with schedule A (28-day dosing). If no dose limiting toxicities (DLTs) are observed then the next cohort of 3 patients will be treated at next higher dose level. If one DLT is observed then 3 more patients will be treated at the same dose level. At anytime if 2 or more DLTs are observed within 3 or 6 patients at dose level 1, then schedule A is considered too toxic and will be abandoned. Patient enrollment will then be resumed using dose level 1 of dosing schedule B (21-day dosing) to determine the MTD. The purpose of schedule B is to prepare for the scenario that dosing schedule A is not tolerable.

Table 1

	Dosing Schedule A	Dosing Schedule B
Dose level 1	1 mg orally on days 1-28	1 mg orally on days 1-21
Dose level 2	2 mg orally on days 1-28	2 mg orally on days 1-21
Dose level 3	3 mg orally on days 1-28	3 mg orally on days 1-21
Dose level 4	4 mg orally on days 1-28	4 mg orally on days 1-21

Dose escalation will continue in 1 mg increments until the MTD is reached. Once the MTD has been determined, an additional 6 patients will be treated at this dose level.

An additional 6 patients will be treated at the MTD.

Dosing will be each night at approximately the same time. Pomalidomide should be taken with a glass of water on an empty stomach. **Only enough pomalidomide for one cycle of therapy will be supplied to the patient each cycle.**

Patients will continue receiving treatment with pomalidomide until disease progression or unacceptable toxicity develops.

Patients are to receive oral aspirin (325mg) as prophylactic anti-thrombotic treatment unless it is contraindicated, or the patient has a platelet count of less than 50,000. If the patient is intolerant of aspirin and has a platelet count of 50,000 or greater, the investigator is to prescribe therapeutic dose warfarin or low molecular weight heparin.

Pomalidomide capsules should be swallowed whole, and should not be broken, chewed or opened. Pomalidomide should be taken without food, at least 2 hours before or 2 hours after a meal.

If a dose of pomalidomide is missed, it should be taken as soon as possible on the same day. If it is missed for the entire day, it should not be made up, rather it should be taken at the next scheduled time point.

Patients who take more than the prescribed dose of pomalidomide should be instructed to seek emergency medical care if needed and contact study staff immediately.

